	Screening	V1 (enrollment)	V2	V3	V4
Time (weeks)		1	4	8	12
Consent		X			
Inclusion/exclusion	X	X			
Study review	X	X			
ACT		X	X	x	X
Physical Exam		X			
FeNO		X			X
Spirometry (pre/post bd)		X			X
IOS (pre/post bd)		X			X
Adherence counseling		X	X	X	
Daily diary review		X	X	X	
Medication distribution		X	X	X	
Classification confirmation		X			X
Co-morbid Medical Questionnaire (GSAS,SSS)			X		
Vocal Handicap Index					X
Respiratory questionnaire (ASUI)		X			X
Mental Health Questionnaires (SF12V2, PHQ, PCL)		x			x
MMRC Dyspnea Scale		X			X
VCD assessment					X
MCT				X	
Pregnancy test		X		X	
Blood		X			
AE screen			X	X	X
Leicester Cough Questionnaire				X	
Urine Sample for Cotinine				X	
6 minute walk test				x	

- Patients who have uncontrolled LRS at V1, but do not fit criteria for Step 3,4 or 5 asthma therapy according to NIH EPR III asthma guidelines will be deferred from the study until they have been seen by their physician and tried on ICS therapy.
- Patients who had symptoms at monitoring visit but are now controlled at V1 will be asked to continue their current treatment (or no treatment) and will continue with the study. They will not be provided with any medications.

Study medication will be provided as open label high dose ICS/LABA diskus (fluticasone /salmeterol; 500/50 mcg; 1 inhalation twice daily, or MDI 230/21, 2 puffs bid) for a 1 month period. Inhaler training and adherence counseling will be performed. Patients will be instructed to maintain a daily diary.

Adherence visit (V2) Patients will return for a monthly visit. At this visit the study will be reviewed, inhaler technique reviewed, and adherence counseling administered. Notation of the counter denoting actuation of the ICS/LABA diskus will be made to assess adherence. Daily diary will be reviewed. Patients will be queried for any adverse effects. Questionnaires to assess co-morbid conditions of chronic rhinosinusitis, and gastroesophageal reflux (GER) will be administered as well as the ACT to assess for control status

Adherence visit (V3) This visit will be similar to V2, however, a methacholine challenge test with lung volumes and oscillometry will also be performed on all patients. Patients will complete the Leicester Cough Questionnaire at Visit 3. Urine will be obtained for cotinine measurements. as well as the ACT to assess for control status

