Classification visit (V4): After 3 months, patients will return for their Classification. At this visit, medication use will be reviewed by noting the medication actuations, and ACT and disease-specific questionnaires for asthma control (ASUI) will be completed^{78, 79}. Screening instruments for post-traumatic stress disorder (PTSD), depression and anxiety will be completed. Blood will be obtained for total and allergen specific IgE, peripheral eosinophil measurements, and measurements of serum periostin and C-reactive protein. FeNO, pre and post BD spirometry and IOS will be performed. Patients will complete a 6 minute walk test. Patients will also undergo laryngoscopy and vocal cord assessment. If patients are unable to complete the vocal cord assessment on the same day as V4, they will be asked to return for a separate visit within two weeks of the end of study (Day 76-90) and will be compensated \$100 for this additional time and effort.

Control Classification. Patients will be classified as ULRS or CLRS based on the ACT score obtained at V4.

Specific Aim 2. To test the hypothesis that discrete measures of lung physiology are associated with patients in the WTC EHC with ULRS compared to CLRS.

Preliminary data pertinent for SA2.

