Sample size estimation

Our primary outcome will be the rate of LRS and CLRS after the 3 month adherence period (SA1). We base our sample size and recruitment on our initial analysis of the WTC EHC monitoring in which 88% of patients who had ever received ICS or ICS/LABA had an ACT score of ≤ 19 . We assume however, that many of these patients were either no longer using medication at the time of the assessment, were on minimal dose, or were non-adherent. Thus we predict by V4 that we will have a 60% rate of ULRS and a total of 200 patients would yield 120 patients who will fit criteria as ULRS and 80 as CLRS. To take into account potential screen failures and dropouts, we will approach 300 patients initially to obtain the total sample size of 200. We will include drop-outs in our intention to treat analysis as these patients can be considered for baseline analysis.

For categorical endpoints, such as BHR, PTSD and PVDMM, the sample sizes of 120 in ULRS group and 80 in CLRS group will achieve 80% power to detect an odds ratio of 2.08 at significance level of 0.05, assuming that the rate of disease is 30% in the CLRS group. A logistic regression of the ULRS vs. CLRS on a continuous,

normally distributed variable (such as depression score or log-FeNo) with a sample size of 200 observations will achieve 80% power at a 0.05 significance level to detect an OR of 1.498 for 1- standard deviation (SD) difference in the continuous covariate.

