Immunosuppression: Potential worsening of infections (e.g., existing tuberculosis, fungal, bacterial, viral, or parasitic infection; ocular herpes simplex) can occur with prolonged use. We use with caution in patients with these infections and will screen you for some of these questions by questionnaire before including you in the study. More serious or even fatal course of chickenpox or measles can occur in susceptible patients.

Hypercorticism and adrenal suppression: May occur with very high dosages or at the regular dosage in susceptible individuals.

Paradoxical bronchospasm (increase in asthma symptoms): We will discontinue Advair Discus and institute alternative therapy if paradoxical bronchospasm occurs.

Patients with cardiovascular or central nervous system disorders: We will screen you with an electrocardiogram before enrolling you in this study and will use with caution because of beta-adrenergic stimulation.

Metabolic effects: We will screen for many of these conditions in our initial evaluation but will be alert to eosinophilic conditions, hypokalemia, and hyperglycemia. We will screen for these coexisting conditions and use with caution in patients with convulsive disorders, thyrotoxicosis, diabetes mellitus, and ketoacidosis.

In addition, long-acting beta2-adrenergic agonists (LABAs), such as salmeterol, one of the active ingredients in ADVAIR DISKUS, can increase the risk of asthma-related death. Currently available data are inadequate to determine whether concurrent use of inhaled corticosteroids or other long-term asthma control drugs mitigates the increased risk of asthma-related death from LABAs but recommendations are now to prescribed LABA only with an inhaled corticosteroid, which is why we use the combination treatment.

According to current recommendations for use, we only prescribe ADVAIR DISKUS for patients not adequately controlled on a long-term asthma control medication, such as an inhaled corticosteroid, or whose disease severity clearly warrants initiation of treatment with both an inhaled corticosteroid and a LABA. We are including you in this study because your asthma or lower respiratory symptoms have not been controlled.

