Methacholine Challenge. Methacholine Challenge will not be done in anyone with current asthma or breathing problems (such as asthma causing shortness of breath or chest discomfort or wheezing on the day of the test) or low lung function. We will also not do a methacholine challenge test if you already have a response to bronchodilator on your spirometry test. The methacholine challenge will only be done after a breathing test measures your lung function to be above 70%. Methacholine challenge will not be done in anyone with known allergy to methacholine. There may be other reasons you cannot take this test. The study doctor will discuss this with you. There are other medical conditions that are affected by methacholine. If you have such a condition, your study doctor must approve of you taking the test.

This test is not likely to cause serious symptoms. Some people have coughing or a tight sensation in their chest from breathing the methacholine, but it is usually mild. About 1 in 4 subjects having this test notice some cough or shortness of breath and about 1 in 10 notices some wheezing. However, reaction to methacholine can include severe bronchoconstriction (such as a severe asthma attack) and loss in breathing function. If you develop an asthma episode during any of this procedure, we will stop the procedure and provide you with albuterol to improve your breathing. This will be provided by a physician involved in the study and you will be checked until your breathing has returned to its baseline.

Blood test. Blood will be obtained by venipuncture. We will collect a blood sample that we will store and test for markers of inflammation as part of this research study. Blood will be drawn from a vein in the arm by usual venipuncture. The risks associated with a venipuncture procedure may include pain, bruising, swelling and/or infection where the needle is put in the vein. The total amount of blood to be drawn will be 30 ml (2 tablespoons).

Vocal Cord Assessment. The vocal cord assessment involves the placement of a small camera through the nose. This is typically done after numbing the nose with topical oxymetazoline (decongestant) and topical 4% lidocaine delivered via an atomizer. The risks are nasal bleeding and discomfort with the spray. Allergies are very rare, but are possible.

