If you do experience a reaction to the medication, treatment will be administered until your condition returns to normal. The placement of the camera can result in minor discomfort in the nose for about 1-2 minutes (the typical length of the exam). Rarely (<1% of the time), there may be some minor bleeding from the nose after the exam is complete. This is usually limited and can be treated easily by the physician seeing you at the time. Patients may experience lower respiratory symptoms due to the presence of the laryngoscope and during the exercise challenge.

The vocal cord assessment will take place at the NYU Voice Center, located at [name]. Patients will be accompanied by study staff member to the NYU Voice Center. If a patient is unable to walk to the NYU Voice Center from Bellevue Hospital for any reason, a taxi will be provided at no cost to the patient.

Protection Against Risks

Protection against risks from specific procedures are described above. Furthermore, personnel will be appropriately trained in the identification and reporting of adverse events to the study doctor to minimize any potential risks or discomfort. If adverse events are reported, study will be delayed until the study doctor may determine the safest course of action, which may include withdrawal of the subject under monitoring of WTC EHC physicians. If patients experience adverse mental health events, patients may be referred to WTC EHC mental health services.

Potential Benefits to the Subjects

There are potential benefits to the subjects. This research study may change the treatment that the patient would otherwise receive. Patients will be provided with a summary of results to bring to their health care

provider that will include the results of their breathing studies, methacholine challenge test, and vocal cord assessment. This may help the health care provider to guide his or her therapy.

Investigator's Qualifications & Experience

Please see attached documents.

Subject Identification, Recruitment and Consent/Assent

Method of Subject Identification and Recruitment

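### Withdrawal after an adverse event is allowed without saying from what, and nothing keeps such subjects for the V4 ACT that alone defines the primary outcome

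*Combined protocol and SAP*

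**What the plan says.** Four parts of the combined protocol and SAP bear on this.

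- **Risk/Benefit Assessment, Protection Against Risks.** The first step is a pause: "If adverse events are reported, study will be delayed until the study doctor may determine the safest course of action". Among the options then open to the doctor is one that the protocol words as follows: "which may include withdrawal of the subject under monitoring of WTC EHC physicians". Withdrawal is thus discretionary, and what the subject is withdrawn from is not stated.
- **Risk/Benefit Assessment, the drug and methacholine paragraphs.** These name what is stopped. For the drug: "We will discontinue Advair Discus and institute alternative therapy if paradoxical bronchospasm occurs". For an asthma episode during the challenge: "we will stop the procedure and provide you with albuterol to improve your breathing". Neither says whether the patient then continues to V4.
- **Methods & Procedures, Control Classification.** "Patients will be classified as ULRS or CLRS based on the ACT score obtained at V4". The ACT is also scheduled at V1, V2 and V3 (for V2 the questionnaires "will be administered as well as the ACT to assess for control status"), but no rule uses those scores to classify a patient whose V4 score is missing.
- **Sample size estimation.** The primary outcome is the split between uncontrolled and controlled patients after three months, predicted as 120 ULRS and 80 CLRS. On drop-outs: "We will include drop-outs in our intention to treat analysis as these patients can be considered for baseline analysis". The stated use is baseline only.

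**The concern.** Read together, these parts leave a route by which a patient has an adverse event, is handed back to the programme's physicians, and never receives a ULRS or CLRS label. That patient then contributes to neither the primary rate nor the comparisons in Specific Aims 2 to 4.

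The loss may not be random. The risk section names worse breathing when inhalers are withheld, paradoxical bronchospasm, and severe bronchoconstriction after methacholine. The ACT is a symptom-based control score, so a patient withdrawn for respiratory worsening is plausibly one who would have scored as uncontrolled. Methacholine is given at V3, one visit before classification, so a patient withdrawn after a reaction could have BHR information but no control status, and would drop out of SA2.a. An ACT that was never taken cannot be recovered in the analysis.

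**Working it through.** **Inputs from Sample size estimation.** N = 200; predicted ULRS rate 60%; BHR 30% in CLRS; odds ratio (OR) 2.08.

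**Assumed inputs, because the documents give none.** Withdrawals w = 10 or 20 (5% or 10% of 200); 90% of them would-be ULRS; 70% to 90% of all withdrawn patients with BHR.

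**1. The plan's own split.** 0.60 × 200 = 120 and 0.40 × 200 = 80, as printed. BHR in ULRS implied by OR 2.08 is 2.08 × 0.30 / (0.70 + 2.08 × 0.30) = 0.624 / 1.324 = 47.1%. The planned table is therefore:
- ULRS: 56.6 with BHR, 63.4 without
- CLRS: 24 with BHR, 56 without

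**2. ULRS rate among classified patients** = (120 − 0.9w) / (200 − w).
- w = 10: 111 / 190 = 58.4%
- w = 20: 102 / 180 = 56.7%
- All losses ULRS: 110 / 190 = 57.9%; 100 / 180 = 55.6%
- Losses in the 60/40 mix: 114 / 190 = 60.0%; 108 / 180 = 60.0%

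For scale, the 95% half-width at N = 200 is 1.96 × √(0.6 × 0.4 / 200) = 6.8 points. The shifts at 90% ULRS are 1.6 and 3.3 points.

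**3. BHR odds ratio, withdrawal depending on both control status and BHR.** Remove 0.9w from ULRS and 0.1w from CLRS, with the same BHR share b in both.

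| w | b | ULRS with / without BHR | CLRS with / without BHR | OR |
|---|---|---|---|---|
| 10 | 0.7 | 50.3 / 60.7 | 23.3 / 55.7 | 1.98 |
| 10 | 0.9 | 48.5 / 62.5 | 23.1 / 55.9 | 1.88 |
| 20 | 0.7 | 44.0 / 58.0 | 22.6 / 55.4 | 1.86 |
| 20 | 0.9 | 40.4 / 61.6 | 22.2 / 55.8 | 1.65 |

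These use the rounded 56.6 and 63.4. With the unrounded 56.56 and 63.44 the second row is 1.87 and the others are unchanged.

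**4. BHR odds ratio, withdrawal depending on one factor only.** If only BHR matters, the 10 or 20 losses come from the 56.6 + 24 = 80.6 patients with BHR in proportion, 56.6 / 80.6 = 70.2% of them ULRS. Both BHR-positive cells shrink by the same factor, so the OR stays at 2.08. The ULRS rate becomes (120 − 7.02) / 190 = 59.5% or (120 − 14.04) / 180 = 58.9%. If only control status matters, both cells within a group shrink by the same factor, and the OR is again 2.08.

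**The case against.** A reader might infer that the protocol removes subjects from the study after an adverse event, so that the V4 ACT is lost in uncontrolled patients and the BHR odds ratio is pulled towards 1. The documents do not support that.

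- Withdrawal is discretionary and comes after a delay. Its object is unstated, so study withdrawal is a reading, not the text.
- The named respiratory harms already have narrower responses: restarting medication and rescheduling, a bronchodilator, stopping the drug, or stopping the procedure. The withdrawal clause can fairly be read as a general back-up.
- Selective loss is inference. It is plausible for respiratory worsening but not shown for oral candidiasis, venipuncture or nasal bleeding. Laryngoscopy events fall at V4 or within a separate visit close to it, when the ACT is due anyway. Methacholine is not given to patients with breathing problems that day, low lung function or a bronchodilator response.
- The odds ratio does not move if withdrawal depends on BHR alone, which is what a methacholine reaction most directly suggests. Larger attenuation (1.93 to 1.81 with 10 withdrawn, 1.77 to 1.53 with 20) appears only if withdrawn ULRS patients are given 70% to 90% BHR while withdrawn CLRS patients are left at 30%. Nothing in the plan justifies that asymmetry.
- The ACT at V1 to V3 could support a sensitivity analysis.

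All of this stands and limits the size of the point. It does not close the gap. The drug-stop and procedure-stop paragraphs are also silent on whether the patient goes on to V4, and an earlier ACT is not the three-month outcome.

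**Conclusion.** The point holds as a gap in outcome collection. The plan allows an unspecified withdrawal after an adverse event, does not secure the V4 ACT for those subjects or for those who stop drug or a procedure, and confines drop-outs to baseline analysis.

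The consequence is conditional. If withdrawals follow respiratory worsening, the ULRS rate could be understated by 1.6 to 3.3 points on assumed losses of 5% to 10%, 90% of them ULRS. That is well inside the 6.8-point half-width, but it is a systematic shift that the interval does not reflect. The bias is zero if losses follow the 60/40 mix. The BHR odds ratio falls to about 1.98–1.88 (10 withdrawn) or 1.86–1.65 (20 withdrawn) only when withdrawal depends on both control status and BHR, at the assumed 70% to 90% BHR; otherwise it stays at 2.08. The case for acting rests less on these figures than on the low cost of avoiding the loss.

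**What to change.** Reconcile the drug-stop, procedure-stop and withdrawal statements in Risk/Benefit Assessment so that two decisions are kept apart: stopping drug or a procedure, which is left to the study doctor, and leaving follow-up. State that, unless the subject withdraws consent, the week-12 ACT (in clinic or by telephone) and adverse event status are still collected and used for the ULRS/CLRS classification, with the stop date and reason recorded. Add the matching sentence under Control Classification.

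Flag patients who have stopped study drug and leave them out in a sensitivity analysis. The main analysis keeps them. This fits the existing design, which already classifies patients who were controlled at V1 and received no study drug.

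The cost is a sentence or two, fields for the stop date and reason, and a few extra calls. The downside is that some classified patients will no longer be on study drug, which the flag makes visible. No clinical rule is proposed or changed.
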